### 13.2 Sample Size/Accrual Rate

Between 5-10 patients were initially accrued in each mutation cohort arm for a total of 20 patients. An additional 10 patients in cohorts 1 and 2 will be added for the extension phase of this study. Accrual rate is estimated at 1 patient in each arm every 2 months.

#### PLANNED ENROLLMENT REPORT

Racial Categories	Ethnic Categories				Total
	Not Hispanic or Latino		Hispanic or Latino		
	Female	Male	Female	Male	
American Indian/ Alaska Native	0	0	0	0	0
Asian	3	3	0	0	6
Native Hawaiian or Other Pacific Islander	0	0	0	0	0
Black or African American	3	3	0	0	6
White	12	12	2	2	28
More Than One Race	0	0	0	0	0
Total	18	18	2	2	40

### **13.3 Reporting and Exclusions**

#### **13.3.1 Evaluation of Toxicity**

All patients will be evaluable for toxicity from the time of their first treatment with MLN0128 (TAK-228).

#### **13.3.2 Evaluation of Response**

All patients included in the study must be assessed for response to treatment, even if there are major protocol treatment deviations or if they are ineligible. Each patient will be assigned one of the following categories: 1) complete response, 2) partial response, 3) stable disease, 4) progressive disease, 5) early death from malignant disease, 6) early death from toxicity, 7) early death because of other cause, or 9) unknown (not assessable, insufficient data). [Note: By arbitrary convention, category 9 usually designates the “unknown” status of any type of data in a clinical database.]

All of the patients who met the eligibility criteria (with the possible exception of those who received no study medication) should be included in the main analysis of the response rate. Patients in response categories 4-9 should be considered to have a treatment failure (disease progression). Thus, an incorrect treatment schedule or drug administration does not result in exclusion from the analysis of the response rate. Precise definitions for categories 4-9 will be protocol specific.

All conclusions should be based on all eligible patients. Subanalyses may then be performed on the basis of a subset of patients, excluding those for whom major protocol deviations have been identified (*e.g.*, early death due to other reasons, early discontinuation of treatment, major protocol violations, etc.). However, these subanalyses may not serve as the basis for drawing conclusions concerning treatment efficacy, and the reasons for excluding patients from the analysis should be clearly reported. The 95% confidence intervals should also be provided.

## **14. PROTECTION OF HUMAN SUBJECTS**

Prior to enrollment of each patient, the risks, benefits, and objectives of the study will be reviewed with the participant, including a discussion of the possible toxicities, side effects, and alternative, non-protocol treatment options. The patients will be reminded that participation in this clinical trial is voluntary and the patient may withdraw consent at any time.

Risks: The standard second-line chemotherapy for patients with metastatic/recurrent squamous cell lung cancers is docetaxel. There is a chance that this regimen is less effective than docetaxel. Treatment with MLN0128 (TAK-228) will not absolutely preclude later treatment with docetaxel however.

Benefits: It is hoped that this regimen will prove to be more effective than docetaxel historically. If so, this would add an additional treatment option for patients with stage IV/recurrent squamous

cell lung cancers.

Consent process: Participation in this trial is voluntary. All patients will be required to sign a statement of informed consent which must conform to MSK IRB guidelines.

Costs: Patients will be charged for physician visits, routine laboratory and radiologic studies required for monitoring their condition. Patients will not be billed for the study drug or for the optional biopsies, or for testing performed on the optional biopsy specimens.

Alternatives: Alternative treatment options include standard chemotherapy, best supportive care, or participation in other investigational studies.

Confidentiality: Every effort will be made to maintain patient confidentiality. Research and hospital records are confidential. Patient's names or any other personally identifying information will not be used in reports or publications resulting from this study. Qualified monitors from MSK, the NCI, and the FDA may review patient records as required.

Patient safety: Patients are monitored by physicians and oncology nurses who are very familiar with clinical trials. In the case of an adverse reaction, immediate medical attention is available. In the evenings and weekends, we have a 24 hour urgent care facility for outpatients. The PI or co-PIs will also be available at all times to organize any necessary intervention.

Monitoring of data to ensure safety: this study is to be monitored by institutional IRB. This incorporates an independent data and safety monitoring committee established by arrangement with the National Cancer Institute. The analysis of safety will include all patients. Adverse events, including all toxic effects of treatment, will be tabulated individually and summarized by severity and causality.

## **14.1 Privacy**

It is the responsibility of the Research Staff to ensure that protocol subjects received the Center's Notice of Privacy Practices. If the subject has not received one, MSK personnel must provide a Notice of Privacy Practices and obtain acknowledgment before the subject participates in the study.

MSK's Privacy Office may allow the use and disclosure of protected health information pursuant to a completed and signed Research Authorization form. The use and disclosure of protected health information will be limited to the individuals described in the Research Authorization form. A Research Authorization form must be completed by the Principal Investigator and approved by the IRB and Privacy Board (IRB/PB).

The consent indicates that individualized de identified information collected for the purposes of this study may be shared with other qualified researchers. Only researchers who have received approval from MSK will be allowed to access this information which will not include protected health information, such as the participant's name, except for dates. It is also stated in the Research Authorization that their research data may be shared with other qualified researchers.

**APPENDIX A      PERFORMANCE STATUS CRITERIA**

ECOG Performance Status Scale		Karnofsky Performance Scale	
Grade	Descriptions	Percent	Description
0	Normal activity. Fully active, able to carry on all pre-disease performance without restriction.	100	Normal, no complaints, no evidence of disease.
		90	Able to carry on normal activity; minor signs or symptoms of disease.
1	Symptoms, but ambulatory. Restricted in physically strenuous activity, but ambulatory and able to carry out work of a light or sedentary nature ( e.g. , light housework, office work).	80	Normal activity with effort; some signs or symptoms of disease.
		70	Cares for self, unable to carry on normal activity or to do active work.
2	In bed <50% of the time. Ambulatory and capable of all self-care, but unable to carry out any work activities. Up and about more than 50% of waking hours.	60	Requires occasional assistance, but is able to care for most of his/her needs.
		50	Requires considerable assistance and frequent medical care.
3	In bed >50% of the time. Capable of only limited self-care, confined to bed or chair more than 50% of waking hours.	40	Disabled, requires special care and assistance.
		30	Severely disabled, hospitalization indicated. Death not imminent.
4	100% bedridden. Completely disabled. Cannot carry on any self-care. Totally confined to bed or chair.	20	Very sick, hospitalization indicated. Death not imminent.
		10	Moribund, fatal processes progressing rapidly.
5	Dead.	0	Dead.

## APPENDIX B ELIGIBLE *NFE2L2*, *KEAP1* AND *KRAS* MUTATIONS

The below Appendix B provides support for the inclusion of the *NFE2L2*, *KEAP1* and *KRAS* mutations in this study.

### **Functional *NFE2L2* and *KEAP1* domains**

Nrf2, the transcription factor encoded by *NFE2L2*, is regulated primarily by degradation through a Keap1-dependent ubiquitin-proteasome pathway. Analysis of the Nrf2 protein more than a decade ago identified 6 highly conserved Neh (Nrf2-ECH homology) domains thought to be functionally important (**Figure 1**). Of these 6 domains, the N-terminal Neh2 domain (aa.1-98) was identified as the canonical Keap1 binding site.(1) Subsequent work showed that within the Neh2 domain, two evolutionarily conserved motifs were present- the DLG motif (aa.17-36) residing in the N-terminal region and the ETGE motif (aa.76-82) residing in the C-terminal portion of the domain. Seven lysine residues N-terminal of the ETGE motif at aa.44, 50, 52, 53, 56, 64, and 68 have also been shown to be necessary for Keap1-dependent ubiquitination and degradation of Nrf2.(2) The importance of the DLG and ETGE motifs is presented in the next section.

Keap1 contains a number of conserved domains the most important of which are Bric-a-Brac (BTB, aa.61-179), the intervening region (IVR, aa.179-315), a double glycine repeat or Kelch repeat (DGR, aa.315-598), and the C-terminal region (CTR, aa.598-624) (**Figure 1**). The BTB domain is thought to assist in dimerization of Keap1. The C-terminal DGR-CTR domain (aa.315-624) forms a six-bladed  $\beta$ -propeller structure and is the key Nrf2 binding domain. What follows is a summary of the functional data available for each domain.

### ***Keap1 DGR-CTR domain and the Nrf2 Neh2 domain are the critical Keap1/Nrf2 binding sites***

[figure not shown]
The physical interaction between the DGR-CTR domain in Keap1 and the Neh2 domain in Nrf2 is essential in suppressing Nrf2 activity. Padmanabhan et al. performed a structural analysis of the DGR-CTR domains of mouse Keap1 and the DGR-CTR complex with Nrf2.(3) Functionally, mutations in the CTR domain were found to impair Keap1-mediated repression of Nrf2 transcriptional activity. Mutations in this region also altered localization of Nrf2, leading to increased nuclear accumulation consistent with loss of function of Keap1.

A separate structural analysis of the DGR-CTR domain from Keap1 complexed with the Neh2 domain from Nrf2 confirmed that the binding domains within Neh2 resided in the DLG and ETGE motifs.(4) First, a probe of the binding stoichiometry, binding constant, enthalpy change, and entropy change between Neh2 and DGR-CTR showed a biphasic isotherm curve consistent with a two-site binding model. Padmanabhan et al. demonstrated that a  $\beta$  hairpin comprised of aa.77-82 (corresponding to the C-terminal ETGE motif) is the high-affinity binding site for Keap1, and that it binds to the bottom of the  $\beta$  propeller formed

by DGR-CTR (3). Within Keap1, Arg-380, Arg-415, and Arg-483 appear to bind specifically to the two acidic glutamates in the ETGE motif.(4) Consistent with this, mutations in R415 substituting lysine for arginine and R483 substituting glycine for arginine decreased Neh2 binding affinity by an order of magnitude(3). Other amino acids in the DGR-CTR domain cavity exposed to the ETGE  $\beta$  hairpin include Tyr-525 and Gln-530, Asn-382, Tyr-572, Phe-577, Tyr-334, Ser-363, Ser-602, and Ser-555.

Tong et al. also found that a weaker binding site is present between aa.1-30 which contains the DLG motif. A peptide containing the DLG motif spanning aa.17-36 elicited a spectral change in the 3 arginine residues in the DGR-CTR domain of Keap1, similar to what was observed with the ETGE peptide motif. This region also appears to assist in positioning the intervening lysine residues for efficient ubiquitination(5).

In terms of *KEAP1* mutations found in lung cancer, Padmanabhan identified a G364C and G430C mutation in a lung cancer patient sample and cell line, respectively. Both of these mutant proteins impaired the ability of Keap1 to repress Nrf2 activity, co-immunoprecipitate with Nrf2, and sequester Nrf2 in the cytoplasm relative to WT Keap1. Modeling these mutant forms of Keap1 within the murine DRG-CTR/Nrf2 structural model showed that G364C abolishes Keap1-Nrf2 interaction by altering the conformation of Ser-363. The hydrophobic nature of cysteine was theorized to be unable to fit within the charged vicinity formed by the key arginine and serine residues in the DGR-CTR cavity. Binding was also abolished with the G430C mutation, presumably by a conformational change that prevents interaction with Glu-79 on Nrf2.

**Figure 1.** Key functional domains for Keap1 and Nrf2. The N-terminal Neh2 domain is the binding site for the negative regulator Keap1. This interaction occurs through the Keap1 C-terminal DGR-CTR domain and both N-terminal (DLG-motif), C-terminal (ETGE motif), and intervening domain (lysine residues, in bold).(4)

### ***Keap1 BTB and IVR domains***

The Keap1 BTB domain spanning aa.61-179 is required for homodimerization of Keap1 and for mediating the interaction between Keap1 and Cul3 (forming the E3-ubiquitin ligase complex that degrades Nrf2).(6) Homodimerization appears to be necessary for Keap1 to repress Nrf2 function and to promote Nrf2 ubiquitination.(7) Substitution of the HKVVL sequence (aa.96-100) in the BTB domain with 5 alanine residues abrogated dimerization and did not rescue mice from juvenile mortality when crossed with a *Keap1*-/- background, suggesting that BTB mutations have a dominant negative effect. A separate group found similar results, with a dominant negative BTB construct inhibiting the ability of Keap1 to retain Nrf2 in the cytoplasm.(8)

Lastly, the IVR domain contains 2 cysteine residues and the BTB domain 1 cysteine residue that are critical for Keap1 function, presumably as electrophile sensors (C151, C273, C288). Mutant forms of these residues diminish Keap1 repression of Nrf2 reporter activity in a dominant negative fashion but do not interfere with Keap1 dimerization.

TCGA-60-2709	G81S	ETGE motif	Yes
TCGA-66-2787	G81S	ETGE motif	Yes
TCGA-51-4079	G81V	ETGE motif	Yes
SQ-MAP	E79Q	ETGE motif	Yes
SQ-MAP	E79K	ETGE motif	Yes
SQ-MAP	E79Q	ETGE motif	Yes
SQ-MAP	E79Q	ETGE motif	Yes
SQ-MAP	K487E	Neh1	No
SQ-MAP	V105del	Neh2	No

TCGA-60-2723	L231V	IVR	No
TCGA-33-4538	L310P	IVR	No
SQ-MAP	R204L	IVR	No
TCGA-18-5595	R260Q	IVR	No
TCGA-66-2777	S224Y	IVR	No
TCGA-37-4133	S243C	IVR	No
TCGA-39-5031	R15L	NTR	No

### **Functional *KRAS* mutations**

*KRAS* mutations occur in approximately 25% of all non-squamous NSCLCs. Nearly all *KRAS* mutations occur in codons 12 and 13. Mutations in these codons lead to constitutive activation of *KRAS* by inhibiting its GTPase activity. This leads to activation of the MAP and PI3K/mTOR pathways. Induction of mutant *KRAS* isoforms is oncogenic, and has formed the basis of many of the transgenic lung cancer models in use today. These include models that have demonstrated, as noted above, dependence on the mTOR pathway and glutamine metabolism in the context of KEAP1 loss of function. The below table lists the frequency breakdown of common *KRAS* mutations in NSCLC based on MSK-IMPACT sequencing data from 1,668 patients:

Mutation	Frequency (N=458 KRAS mutations)
G12C	42%
G12V	15%

G12D	13%
G12A	9%
G13D	4%
Q61H	4%
G13C	3.5%
G12S	2.4%

*KEAPI* co-alterations occur in 23% of all *KRAS* mutant lung cancer cases in the MSK-IMPACT dataset, circumscribing a sizable population of patients with both alterations. Specific *KRAS* mutations associated with *KEAPI* alterations include codon 12 alterations (G12A,C,S,V,D), codon 13 alterations (G13C,D,R) and codon 61 (Q61H).

### ***Integral Biomarker Inclusion Criteria***

Based on the preceding analysis, virtually all *NFE2L2* mutations detected to date are predicted to be functionally relevant. This clustering of mutations in specific subdomains of a larger regulatory domain is reminiscent of hotspot mutations in other oncogenes. Only mutations that occur in amino acids listed in **Table 1** should be included in the proposed phase 2 study of MLN0128 (TAK-228).

Eligible *KEAPI* mutations will be prioritized, but not limited, to those alterations that occur in the amino acids listed in **Table 3**.

Eligible *KRAS* mutations will include any missense mutation that occurs in codons 12, 13, and 61.

## APPENDIX C BIOASSAY TEMPLATES

The below Appendix C describes the validation studies for the integral *NFE2L2* and *KEAP1* mutation biomarker testing. The validation study for *KRAS* mutations was previously published as part of the MSK-IMPACT validation study leading to its FDA approval in 2017 as an in vitro diagnostic test to identify genetic mutations across cancers. Please refer to Cheng DT et al. J Mol Diagn 2015 17(3):251-64 (PMID25801521) for the validation study details.

### Validation Study of *KEAP1* and *NFE2L2* Mutations

#### Accuracy Study

To carry out this validation, we obtained a total of 23 positive tumor DNA samples (18 *KEAP1* and 5 *NFE2L2*) that had been previously genotyped by our “MSK-IMPACT (Integrated Mutation Profiling of Actionable Cancer Targets): A Hybridization-Capture Based Next Generation Sequencing Assay”. The samples were also studied by Sanger DNA sequencing. All DNA sequencing reactions were performed in both forward and reverse directions.

Concordant results were obtained for all 23 samples by DNA sequencing and MSK-IMPACT assay. The results of the validation study are summarized in **Tables 1 & 2**.

### **Precision and Reproducibility Study**

The precision and reproducibility studies were extensively performed in the initial MSK-IMPACT validation according to NGS NYSDOH guidelines (attached). In addition, two DNA samples, one *KEAP1* positive and one *NFE2L2* positive, were studied in triplicate in the same run for the intra-assay precision study. The same DNA samples were also studied over three different runs for the inter-assay reproducibility study. Concordant results were obtained for both intra- and inter-assay reproducibility studies. Replicates tested within the same run were assigned different barcodes to ensure reproducibility of results regardless of sample/barcode combination. Each replicate was assigned a different barcode (bc). Differences in barcodes, coverage depth, allele depth (AD) and variant frequency (VF) for the known variant across intra- and inter- run replicates are listed in **Tables 3.1 & 3.2**.

#### **3.1) Precision and reproducibility studies of *KEAP1***

Table 3.1A: Total number of mutations called across all 340 genes, for *KEAP1* intra- (precision) and inter-run (reproducibility) replicates.

Sample	Total Number of Mutations called across all 340 genes	Normal sample used
7555-13-1A	13	Matched
7555-13-1B	13	Matched
7555-13-1C	13	Matched
7555-13-2	13	Matched
7555-13-3	13	Matched

Table 3.1B-i: Differences in Illumina TruSeq barcode, coverage, allele depth and variant frequency for the known variant detected in each inter-run (reproducibility) replicate.

Sample	cDNA change	AAchange	Validation Run	Barcode	Coverage	AD	VF	Normalized DP
7555-13-1A	c.811G>A	p.V271M	KEAP1 Intra	bc34	910	483	0.42	1.26
7555-13-1B	c.811G>A	p.V271M	KEAP1 Intra	bc36	1011	506	0.42	1.19
7555-13-1C	c.811G>A	p.V271M	KEAP1 Intra	bc38	1185	688	0.44	1.33

Table 3.1B-ii: Differences in Illumina TruSeq barcode, coverage, allele depth and variant frequency for the known variant detected in each intra-run (precision) replicate.

Sample	cDNA change	AA change	Validation Run	Barcode	Coverage	AD	VF	Normalized DP
7555-13-1A	c.811G>A	p.V271M	KEAP1 Inter	bc34	910	483	0.42	1.26
7555-13-2	c.811G>A	p.V271M	KEAP1 Inter	bc24	1078	517	0.40	1.19
7555-13-3	c.811G>A	p.V271M	KEAP1 Inter	bc43	1044	560	0.43	1.25

### 3.2) Precision and reproducibility studies of *NFE2L2*

Table 3.2A: Total number of mutations called across all 340 genes, for *NFE2L2* intra- (precision) and inter-run (reproducibility) replicates.

Sample	Total Number of Mutations called across all 340 genes	Normal sample used
5155-14-1A	10	Matched
5155-14-1B	10	Matched
5155-14-1C	10	Matched
5155-14-2	10	Matched
5155-14-3	10	Matched

Table 3.2B-i: Differences in Illumina TruSeq barcode, coverage, allele depth and variant frequency for the known variant detected in each inter-run (reproducibility) replicate.

	cDNA change	AA change	Validation Run	Barcode	Coverage	AD	VF	Normalized DP
5155-14-1A	c.76C>A	p.Q26K	NEF2L2 Intra	bc39	702	555	0.53	1.51
5155-14-1B	c.76C>A	p.Q26K	NEF2L2 Intra	bc40	693	537	0.51	1.51
5155-14-1C	c.76C>A	p.Q26K	NEF2L2 Intra	bc42	621	491	0.52	1.53

Table 2.2B-ii: Differences in Illumina TruSeq barcode, coverage, allele depth and variant frequency for the known variant detected in each intra-run (precision) replicate.

	cDNA change	AA change	Validation Run	Barcode	Coverage	AD	VF	Normalized DP
5155-14-1A	c.76C>A	p.Q26K	NEF2L2 Inter	bc39	702	555	0.53	1.51
5155-14-2	c.76C>A	p.Q26K	NEF2L2 Inter	bc38	742	545	0.51	1.45
5155-14-3	c.76C>A	p.Q26K	NEF2L2 Inter	bc43	596	462	0.55	1.42

## APPENDIX D PATIENT PILL DIARY

A Study to Test if MLN0128 (TAK-228) can Treat Patients with Non-Small Cell Lung Cancers with *NFE2L2* and *KEAP1* Mutations

Name: \_\_\_\_\_

MRN: \_\_\_\_\_

### To be completed by NP:

Number of pills dispensed: \_\_\_\_\_ 1mg \_\_\_\_\_ 3mg \_\_\_\_\_ Date: \_\_\_\_\_

Daily dose of MLN0128 (TAK-228): \_\_\_\_\_ mg Cycle : \_\_\_\_\_

Pill bottle returned: circle Yes or N

### Instructions for patient:

1. You will be given a pill diary to record the time and doses of MLN0128 (TAK-228) you take each day. This diary along with any leftover pills and the pill bottles should be brought to each visit with your study doctor.
2. MLN0128 (TAK-228) should be taken once daily, at approximately the same time every day.
3. Take MLN0128 (TAK-228) on an empty stomach at least 2 hours after a meal. Do not eat or drink (except water) for at least 1 hour after taking MLN0128 (TAK-228).
4. Each dose should be taken with a glass of water and consumed whole (no chewing). The capsules should not be opened, chewed, or crushed. If multiple capsules are required for each dose, they should be taken at the same time.
5. If you miss a dose, you can still take that dose if it has been less than 12 hours since you missed the dose.
6. If you vomit after taking the pill, do not replace that dose. If you can see that the pill has come up, mark the dose as missed in the comments.

Cycle	Date	Time (circle one)	Amount (mg)	Comments
Day 1		AM/PM		
Day 2		AM/PM		
Day 3		AM/PM		
Day 4		AM/PM		
Day 5		AM/PM		
Day 6		AM/PM		
Day 7		AM/PM		
Day 8		AM/PM		
Day 9		AM/PM		
Day 10		AM/PM		
Day 11		AM/PM		
Day 12		AM/PM		
Day 13		AM/PM		
Day 14		AM/PM		
Day 15		AM/PM		
Day 16		AM/PM		
Day 17		AM/PM		
Day 18		AM/PM		
Day 19		AM/PM		

Day 20		AM/PM		
Day 21		AM/PM		
Day 22		AM/PM		
Day 23		AM/PM		
Day 24		AM/PM		
Day 25		AM/PM		
Day 26		AM/PM		
Day 27		AM/PM		
Day 28		AM/PM		

Patient signature: \_\_\_\_\_ Date: \_\_\_ / \_\_\_ / \_\_\_

Consenting professional / NP signature: \_\_\_\_\_ Date: \_\_\_ / \_\_\_ / \_\_\_

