### 5. TREATMENT PLAN

#### 5.1 Agent Administration

Treatment will be administered on an outpatient basis. Reported adverse events and potential risks are described in Section 7. Appropriate dose modifications are described in Section 6. No investigational or commercial agents or therapies other than those described below may be administered with the intent to treat the patient's malignancy.

Regimen Description					
Agent	Premedications; Precautions	Dose	Route	Schedule	Cycle Length
MLN0128 (TAK- 228)	none	3mg	oral	daily continuous	28 days (4 weeks)

Patients will be treated MLN0128 (TAK-228) 3mg oral daily continuously on an every 4 week schedule. MLN0128 (TAK-228) will be taken at the same time every day. The capsules should not be opened, chewed, or crushed. The patient will be given a medication diary at the beginning of each cycle of therapy. The medication diary, along with the pill bottles and any unused drug, will be returned to the clinic staff at the end of each cycle.

In cases where a subject misses dosing at his/her dosing time, the subject may still take the dose within 12 hours of the regular dosing time (subjects should not take 2 consecutive daily doses within 12 hours of each other). Subjects who vomit shortly after receiving MLN0128 (TAK-228) will not

receive a replacement dose. If confirmed that the study drug has been vomited, the dose should be noted as having been missed.

If severe emesis or mucositis prevents the patient from taking scheduled doses, that dose will be skipped. If emesis occurs after study medication ingestion, the dose will not be readministered, and patients should resume dosing at the next scheduled time with the prescribed dosage. Patients should record the occurrence of the emesis in their dosing diaries. Under no circumstance should a patient repeat a dose or double-up doses.

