### **In-Home Daily Fasting Glucose Monitoring**

In addition to obtaining fasting glucose levels at the clinic visits as outlined in the Schedule of Events, all patients will be given a prescription for a glucometer to monitor their daily FBG levels at home. The level should be collected daily, predose on dosing days, and at approximately the same time each day.

On Cycle 1 Day 1, the patient will be provided an in-home glucometer. Patients should be trained on proper use of the glucometer and instructed to collect a daily FBG level every morning (predose on dosing days), starting on Cycle 1 Day 2. Patients will be instructed to bring the glucometer with them to each study visit so that the data collected can be reviewed and recorded in the source documents.

Investigators will be responsible for reviewing the home glucose monitoring logs for hyperglycemia. The patient will be instructed to contact the site immediately if the value is abnormal (ie,  $\geq 150$  mg/dL) for further instructions on the management of their hyperglycemia. Hyperglycemia observed during home glucose monitoring should be confirmed in the clinic.

If no irregularities in the fasting blood glucose level are observed during a minimum of 2 consecutive months, then the frequency of in-home fasting blood glucose testing can be reduced to a minimum frequency of once weekly, depending on the investigator's judgment and approval. Patients will continue to notify the investigator of fasting blood glucose levels that exceed 150 mg/dL and, if blood glucose levels are not well controlled, or if the patient requires either oral hypoglycemic agents or insulin to control blood glucose levels, then the frequency of in-home testing of FBG levels will be reinstated to daily.

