## 6. DOSING DELAYS/DOSE MODIFICATIONS

Toxicities will be graded using the NCI CTCAE Version 4.0 and dose modifications of the study drugs will be made for hematologic and other toxicities. Patients experiencing study drug related toxicities that require a delay in dosing for >21 days will be discontinued from further participation in this study. In the event that patients must have treatment delayed with a treatment cycle due to toxicities, those doses held during a cycle will not be made up.

Dose Level	MLN0128 (TAK-228) Dose
0	3 mg flat dose daily continuous
-1	2 mg flat dose daily continuous
-2	2 mg daily 5 days/ week
-3	1 mg 5 days/week
-4	Withdraw from study

Treatment Modification for MLN0128 (TAK-228)-Related Adverse Events		
Event	CTCAE. V4 Grade	Action to be Taken
QTc prolongation	≥ Grade 3 or > 60ms change from baseline on at least two separate ECGs	
First Occurrence:
 
 
• Omit MLN0128 (TAK-228) dose
 
• Perform an analysis of potassium and magnesium, and if below lower limit of normal, correct with supplements to within normal limits. Concomitant medication usage must be reviewed.
 
• Perform a repeat ECG within one hour of the first QTcF of 500 ms
 
• If QTcF remains > 500 ms, repeat ECG as clinically indicated, but at least once a day until the QTcF returns to < 480 ms. Seek cardiologist input
 
• Once QTcF prolongation has resolved, MLN0128 (TAK-228) may be restarted at a one lower dose level
 
 
Second Occurrence:
 
 
• Permanently discontinue patient from the study treatment
 

	Other Cardiac Events	Grade 1-2
	Grade 3	
Omit dose of MLN0128 (TAK-228) until resolved to ≤ Grade 1
 
 
• If resolved within 7 days, then resume at same dose level of MLN0128 (TAK-228).
 
• If resolved in >7 days, resume at ↓1 dose level of MLN0128 (TAK-228).
 
• If not resolved in 21 days, then discontinue patient from study treatment.
 

	Grade 4	Permanently discontinue patient from the study treatment
Treatment Modification for MLN0128 (TAK-228)-Related Adverse Events		
Event	CTCAE. V4 Grade	Action to be Taken
ENDOCRINE		

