### Directions:

- You will need to perform the glucose monitoring test on a daily basis, predose on dosing days, and at approximately the same time each day- prior to breakfast. **You are required to fast for at least 8 hours prior to testing.** Fasting means not eating or drinking any liquids (with the exception of water).
- In the log, please write in the date, note the time you completed the glucose test, whether you fasted or not (fed state) before the test, and your glucose levels as provided by your glucometer.
- Please contact the site immediately if the value is abnormal (ie,  $\geq 150$  mg/dL) for further instructions on the management of their hyperglycemia. Hyperglycemia observed during home glucose monitoring should be confirmed in the clinic.

Site Contact Name: \_\_\_\_\_

Site Contact: Number: \_\_\_\_\_

Day	Date	Approximate time of Test (Circle AM or PM)	Fasting or Fed (Circle One)	Glucose Test Results (mg/dL)
Day 1		____ : ____ am / pm	Fasting or Fed	
Day 2		____ : ____ am / pm	Fasting or Fed	
Day 3		____ : ____ am / pm	Fasting or Fed	
Day 4		____ : ____ am / pm	Fasting or Fed	
Day 5		____ : ____ am / pm	Fasting or Fed	

Day 6		____:____ am / pm	Fasting or Fed	
Day 7		____:____ am / pm	Fasting or Fed	
Day 8		____:____ am / pm	Fasting or Fed	
Day 9		____:____ am / pm	Fasting or Fed	
Day 10		____:____ am / pm	Fasting or Fed	
Day 11		____:____ am / pm	Fasting or Fed	
Day 12		____:____ am / pm	Fasting or Fed	
Day 13		____:____ am / pm	Fasting or Fed	
Day 14		____:____ am / pm	Fasting or Fed	
Day 15		____:____ am / pm	Fasting or Fed	
Day 16		____:____ am / pm	Fasting or Fed	
Day 17		____:____ am / pm	Fasting or Fed	
Day 18		____:____ am / pm	Fasting or Fed	
Day 19		____:____ am / pm	Fasting or Fed	
Day 20		____:____ am / pm	Fasting or Fed	
Day 21		____:____ am / pm	Fasting or Fed	
Day 22		____:____ am / pm	Fasting or Fed	
Day 23		____:____ am / pm	Fasting or Fed	
Day 24		____:____ am / pm	Fasting or Fed	
Day 25		____:____ am / pm	Fasting or Fed	
Day 26		____:____ am / pm	Fasting or Fed	
Day 27		____:____ am / pm	Fasting or Fed	
Day 28		____:____ am / pm	Fasting or Fed	

Patient Signature: \_\_\_\_\_ Date: \_\_\_\_\_

Investigator Signature: \_\_\_\_\_ Date: \_\_\_\_\_

**APPENDIX F      LIST OF RELEVANT CYTOCHROME P450 INHIBITORS  
AND INDUCERS**

---

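### The pill diary tells every patient to dose every day, but dose levels -2 and -3 are five-days-a-week schedules; followed as printed, level -2 becomes level -1 (14 mg a week instead of 10) while capsules last

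*Combined protocol and SAP*

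**What the plan says.** The dose-level table in Section 6 starts patients at 3 mg every day (level 0) and steps down to 2 mg every day (level -1), then "2 mg daily 5 days/ week" (level -2), then "1 mg 5 days/week" (level -3). After that the patient leaves the study.

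Section 5.1 states how the diary is issued: "The patient will be given a medication diary at the beginning of each cycle of therapy". Appendix D is the only pill diary in the documents. Item 2 of its patient instructions reads "MLN0128 (TAK-228) should be taken once daily, at approximately the same time every day". Its grid runs from Day 1 to Day 28, with columns for date, time, amount and comments. The part completed by staff has "Number of pills dispensed" (by capsule strength), a date, a daily dose in mg, a cycle number and whether the bottle came back. Nothing on the form carries a weekly schedule, and nothing tells staff to adapt it for the reduced levels.

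The glucose material does allow for days without drug. Section 5.2 says "The level should be collected daily, predose on dosing days, and at approximately the same time each day", and the log in Appendix E tells the patient to "perform the glucose monitoring test on a daily basis, predose on dosing days".

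**The concern.** The mg per dose is the same at levels -1 and -2, so the days off are the whole of that reduction. The diary's one dose field reads 2 mg at both levels, and its printed instruction describes level -1. A patient reduced to level -2 is therefore handed a sheet that tells them to keep taking the level -1 dose.

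Under Section 6 reductions are made one level at a time for drug-related toxicity, so a patient normally reaches level -2 after two of them. If the sheet is followed, the second reduction does nothing to the weekly dose while capsules last. The clinic may explain the days off when treatment restarts, but that explanation would contradict the form the patient uses at home. There is also a recording problem: a blank row does not separate a planned day off from a missed dose unless someone writes it in the comments.

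The form is still in use. Section 13.1 extends accrual by 10 patients in each of cohorts 1 and 2.

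**Working it through.** **Inputs.** Dose and days per week at each level come from the Section 6 table. The cycle is 28 days, or 4 weeks (Section 5.1). Daily dosing is taken from Appendix D, item 2. Capsules come as 1 mg and 3 mg (Section 8.1.1), so 2 mg is two 1 mg capsules. The documents state no weekly totals, so there is no figure of the plan's own to reproduce.

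**Weekly dose** = mg per dosing day × dosing days per week.

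| Level | Section 6, mg/week | Diary as printed, mg/week | Ratio |
|---|---|---|---|
| 0 | 3 × 7 = 21 | 3 × 7 = 21 | 1.00 |
| -1 | 2 × 7 = 14 | 2 × 7 = 14 | 1.00 |
| -2 | 2 × 5 = 10 | 2 × 7 = 14 | 14/10 = 1.40 |
| -3 | 1 × 5 = 5 | 1 × 7 = 7 | 7/5 = 1.40 |

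Level -2 by the diary equals level -1. Level -3 by the diary (7 mg) is still below the intended level -2 (10 mg).

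**Per cycle.** Section 6 gives 5 × 4 = 20 dosing days, so 2 × 20 = 40 mg at level -2 and 1 × 20 = 20 mg at level -3. What a patient dosing daily actually takes is capped by supply. The number of capsules dispensed is recorded but not prescribed, so the counts below are assumptions that show the range. Let N be the number of 1 mg capsules dispensed.

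- Level -2 (N at least 40): total = min(N, 56); excess = (min(N, 56) − 40)/40.
  - N = 40: supply ends after 40/2 = 20 days. The weeks are 14, 14, 12 and 0 mg, total 40 mg. Excess 0%, but the spacing is wrong.
  - N = 48: total 48 mg, excess 8/40 = 20%.
  - N = 56 or more: total 56 mg, excess 16/40 = 40%.
- Level -3 (N at least 20): total = min(N, 28); excess = (min(N, 28) − 20)/20.
  - N = 20: the weeks are 7, 7, 6 and 0 mg, total 20 mg. Excess 0%.
  - N = 28 or more: total 28 mg, excess 8/20 = 40%.

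The one supply figure in the protocol is the 30-capsule bottle (Section 8.1.1). If whole bottles are handed out, which is an assumption, level -2 needs two (60 capsules, against 56 for daily dosing) and level -3 needs one (30, against 28). Both leave room for the full 40%.

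**The case against.** The mismatch in the text and the arithmetic are hard to dispute. The case on the other side is about likelihood and weight.

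- **Other safeguards.** Reductions generally follow a held dose and a restart decided in clinic, so the diary is not the patient's only instruction. Staff fill in the pill count and dose, a professional countersigns the diary, leftover capsules come back, and the study calendar has examinations in weeks 1, 3, 5 and 9. This makes long, unnoticed daily dosing less likely. None of these steps, however, states which days are dosing days.
- **Supply.** The 14 mg figure holds only while capsules last, and the documents fix no count. This stands, and it is why the per-cycle excess is a range starting at 0%.
- **Frequency.** No rate of first or second reductions is given. The nearest figure, 1 dose-limiting toxicity among 11 patients on the milled 3 mg daily dose (Section 2.3), does not measure later reductions. Level -2 may be rare or never reached. This stands.
- **Section 5.1 also describes dosing at the same time every day.** It does, but it sets out the 3 mg starting regimen and sends the reader to Section 6 for modifications. The diary does neither, and it goes to the patient each cycle whatever the level.
- **The glucose log does not conflict with the diary under daily dosing.** This is correct for levels 0 and -1. The two forms part only at levels -2 and -3. The log's main value here is to show that suitable wording already exists.

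**Conclusion.** The point holds, as a minor one. Appendix D gives an instruction that conflicts with the Section 6 schedules at levels -2 and -3. Followed as printed, it raises the weekly dose by 40% at each of these levels while capsules last, and at level -2 it cancels the reduction from level -1. Over a cycle the excess lies between 0% and 40%.

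This rests on three conditions: a patient reaches level -2 or -3, the form is issued unaltered, and the patient follows the form over anything said in clinic. The documents do not show how often these occur together, and it may be never.

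The consequence is limited. The resulting 14 mg a week is an allowed level and is below the 21 mg starting dose. Actual intake can be recovered from the diary's amount column and the returned capsules. The primary endpoint, the error rates and the sample size are unaffected.

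**What to change.** Change Appendix D only:

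1. Add a schedule field to the staff section: daily, or five days a week with the dosing days marked.
2. Reword item 2 so that the drug is taken once daily on the patient's dosing days, in line with Section 5.2 and Appendix E.
3. Let planned days off be marked in the 28-day grid, so that a blank row means a missed dose.

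The dose levels, Section 5.1 and the statistical section stay as they are. The cost is a one-page revision of the diary at the next amendment.
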